#### **6.3 Surgery**

After completion of SBRT, patients will undergo re-evaluation for resection with a pancreas protocol CT scan, MRI if CT scan can not be tolerated, and PET or EUS if deemed necessary to determine resectability. Those patients who are determined to be potentially resectable will undergo a laparoscopy, followed by surgical resection within 4-12 weeks after completion of SBRT. For surgical resections occurring more than 12 weeks after SBRT, exceptions will be recorded and patients can remain on study with PI approval. Standard pathologic evaluation and staging will be performed.

#### **6.4 Adjuvant therapy**

Post-operatively, patients will be followed every 2 weeks in medical oncology, and receive 4 additional cycles of mFOLFIRINOX to complete a total of 12 cycles, with further dose modifications at the discretion of the treating medical oncologist. Adjuvant chemotherapy will commence within 12 weeks of surgery.

### **7. STUDY DRUGS, DOSE MODIFICATIONS, AND TOXICITY MANAGEMENT**

#### **7.1 Doses and Schedule of Study Drugs**

Chemotherapy will consist of mFOLFIRINOX administered every two weeks, as described in Section 6 at the following doses:

- Oxaliplatin 85 mg/m^2 IV infused over two hours, followed by
- Leucovorin 400 mg/m^2 (or levoleucovorin 200 mg/m^2) IV over two hours
- Irinotecan 135 mg/m^2 IV over 90 minutes (concurrent with leucovorin during the last 90 min of the leucovorin infusion)
- 5-FU 300mg/m^2 IV bolus, then 2400 mg/m^2 continuous IV infusion over 46 hours

#### **7.2 Study Drugs: Formulation, Storage, Availability, Preparation, and Toxicity**

Qualified personnel who are familiar with procedures that minimize undue exposure to themselves and to the environment should undertake the preparation, handling, and safe disposal of chemotherapeutic agents in a self-contained, protective environment. Unused portions of injectable chemotherapeutic agents supplied as single-dose preparations should be discarded within eight hours of vial entry to minimize the risk of bacterial contamination.

The total administered dose of chemotherapy may be rounded up or down within a range of 5% of the actual calculated dose.

### 7.2.1 Oxaliplatin (Eloxatin)

#### *Availability*

Oxaliplatin is commercially available as an aqueous solution in vials containing 50 mg and 100 mg at a concentration of 5 mg/mL. The vials do not contain any preservative and they are intended for single use.

#### *Storage and Stability*

Intact vials should be stored at room temperature. Solutions diluted in D5W are stable for 6 hours at room temperature or 24 hours under refrigeration.

#### *Preparation*

The calculated dose of oxaliplatin should be diluted for infusion with 250 mL to 500 mL D5W. Oxaliplatin should not be diluted with a sodium chloride solution. Needles, syringes, catheters or IV administration sets containing aluminum should not be used with oxaliplatin. As with other platinum compounds, contact with aluminum may result in a black precipitate.

#### *Administration*

Oxaliplatin will be administered by intravenous infusion over 120 minutes in patients receiving FOLFIRINOX. Infusion time may be prolonged (up to 6 hours) in patients experiencing pharyngolaryngeal dysesthesia.

Oxaliplatin is unstable in the presence of chloride or alkaline solutions. Do NOT mix or administer oxaliplatin with saline or other chloride-containing solutions. Do NOT administer other drugs or solutions in the same infusion line. Flush IV lines/catheters with Dextrose 5% in Water both before and after oxaliplatin administration.

#### *Toxicity*

The most commonly observed oxaliplatin toxicities include neurotoxicity, GI toxicity, and myelosuppression. Three neurotoxicity syndromes have been seen:

Acute sensory neuropathy develops within hours to 2 days after oxaliplatin administration. Symptoms include paresthesia, dysesthesia, and hypoesthesia of the hands, feet and perioral regions. Jaw spasm, abnormal tongue sensation, dysarthria, eye pain and a sensation of chest pressure have also been noted. Acute sensory neuropathy symptoms may be exacerbated by exposure to cold temperature or cold objects. Symptoms are reversible, usually resolving within 14 days and commonly recurring with further dosing. This syndrome has been observed in about 56% of patients receiving oxaliplatin with 5-FU and leucovorin.

Acute pharyngolaryngeal dysesthesia is reported to occur in 1-2% of patients. This syndrome is characterized by a subjective sensation of difficulty breathing or swallowing without laryngospasm or bronchospasm or objective evidence of hypoxia. Avoidance of cold drinks, food and air is suggested to order to minimize pharyngolaryngeal dysesthesia. Antianxiety agents (e.g. lorazepam) may be used to treat pharyngolaryngeal dysesthesias once oxygen saturation has been documented to be normal.

Peripheral neuropathy persisting > 14 days is characterized by paresthesias, dysesthesias, and hypoesthesia. Abnormalities in proprioception may also be seen. Symptoms of persistent neuropathy may improve upon discontinuation of oxaliplatin.

Gastrointestinal toxicities include nausea, vomiting (oxaliplatin is considered to be moderately emetogenic) and diarrhea.

Neutropenia is reported in 73% of patients receiving oxaliplatin with 5-FU and leucovorin (44% grade 3 or 4). Grade 3 or 4 thrombocytopenia is reported to occur in 4% of patients receiving the combination.

Allergic reactions, similar to those seen with other platinum compounds, have also been observed in patients treated with oxaliplatin. Reactions range from rash to anaphylaxis

Rarely, oxaliplatin has been associated with pulmonary fibrosis, which may be fatal. Oxaliplatin should be discontinued in the presence of unexplained pulmonary symptoms (e.g. nonproductive cough, dyspnea) or pulmonary infiltrates until interstitial lung disease or pulmonary fibrosis have been ruled out.

Recent reports of oxaliplatin extravasation suggest that tissue necrosis may result and that oxaliplatin should be considered a vesicant. No standard treatment exists for oxaliplatin extravasation although heat and sodium thiosulfate have both been suggested.

Veno-occlusive disease (VOD) of the liver is a rare complication associated with oxaliplatin and 5-FU. Clinical manifestations of VOD include hepatomegaly, ascites, and jaundice. Histologically, VOD is characterized by diffuse damage in the centrilobular zone of the liver. Sequelae of VOD include hepatomegaly, splenomegaly, portal hypertension, and esophageal varices. A recent analysis of resected liver metastases in 153 patients indicated histological findings consistent with VOD in 6/27 patients who received 5-FU alone, 4/17 patients who received 5-FU and irinotecan, 20/27 patients who received 5-FU and oxaliplatin, and 14/16 who received 5-FU, oxaliplatin and irinotecan. The remaining 66 patients had not received chemotherapy prior to resection. There were no such findings in these patients.

For more information on toxicities associated with oxaliplatin, please see the package insert.

### 7.2.2 5-Fluorouracil (5-FU: Fluorouracil: Adrucil®)

Please refer to the package insert for complete product information.

#### *Availability*

5-FU is commercially available as a 50 mg/mL solution for injection in 10 mL, 20 mL, 50 mL and 100 mL vials

#### *Preparation*

Inspect for precipitate: if found, agitate or gently heat in water bath.

Bolus injections are prepared using undiluted drug.

46-48 hour infusion of 5-FU should be prepared for administration via ambulatory infusion pump according to the individual institution's standards. These solutions may be prepared in D5W or 0.9% NaCl. 5 FU should not be mixed in the same solution with most parenteral antiemetics.

***Storage and Stability***

Intact vials should be stored at room temperature and protected from light. Slight yellow discolor does not usually indicate decomposition. Stability in ambulatory pumps varies according to the pump, manufacturer of drug, concentration and diluent. Please refer to appropriate reference sources for additional information.

***Administration***

In this study, 5-FU is administered as a 300 mg/m^2 IV bolus followed by 2400 mg/m^2 by IV infusion over 46 to 48 hours.

***Toxicity***

Nausea, diarrhea, vomiting (mild); stomatitis (5-8 days after treatment initiation); myelosuppression; granulocytopenia (9-14 days); thrombocytopenia (7-14 days); alopecia; loss of nails; hyperpigmentation; photosensitivity; maculopapular rash; palmar-plantar erythrodysesthesias: (42-82% receiving continuous infusion); CNS effects: cerebral ataxia (rare); cardiotoxicity: MI, angina: asymptomatic S-T changes 68%; ocular effects: excessive lacrimation and less commonly, tear duct stenosis.

***Drug Interactions***

Leucovorin enhances the cytotoxicity of 5-FU by forming a more stable tertiary complex with thymidylate synthase. Concomitant administration of 5-FU with warfarin has been reported to result in increased INR/prolonged prothrombin time. Patients receiving both drugs should be followed with weekly INRs.

**7.2.3 Leucovorin Calcium (Folinic Acid; Calcium Folinate; Citrovorum Factor; N 5-Formyltetrahydrofolate; 5-Formyl-FH4; Folinic Acid)**

Levoleucovorin (200 mg/m^2) may be substituted for leucovorin (400 mg/m^2) in this study. Please refer to the package insert for complete product information for levoleucovorin and leucovorin.

***Availability***

Leucovorin calcium is commercially available in: 50 mg, 100 mg, 350 mg vials for reconstitution.

***Storage and Stability***

Intact vials should be stored at room temperature and protected from light. Solutions reconstituted with BWI are stable for at least 7 days at room temperature.

***Preparation***

Leucovorin may be reconstituted with Bacteriostatic Water for Injection (BWI) or with Sterile Water For Injection. Solutions should be further diluted in D5W, 0.9% NaCl or Ringers solution for infusion over two hours.

***Administration***

Leucovorin will be administered as a 400mg/m^2 IV infusion over 2 hours after oxaliplatin administration. Leucovorin may also be administered concurrently with oxaliplatin as a separate IV infusion.

***Toxicity***

The only adverse reactions associated with leucovorin are allergic reactions. These are extremely uncommon.

**7.2.4 Irinotecan (CMT-11, Camptosar)*****Availability***

Irinotecan is commercially available in a concentration of 20mg/mL in 2mL, 5mL, and 25 mL vials.

***Storage and Stability***

Intact vials should be stored at controlled room temperature 59 to 86 degrees Fahrenheit (15 to 30 degrees Celsius) and protected from light. Solutions diluted in D5W are reported to be stable for 48 hours under refrigeration and protected from light. Irinotecan solutions should not be frozen as the drug may precipitate.

***Preparation***

Irinotecan is diluted in 5% dextrose (D5W) 500 mL to a final concentration of 0.12 – 1.1 mg/mL.

***Administration***

In this study, irinotecan is administered by IV infusion over 90 minutes

***Toxicity***

Virtually all phase I and II studies of irinotecan have reported neutropenia and/or late diarrhea (diarrhea occurring more than 24 hours after the irinotecan administration as the dose limiting toxicities (depending on the schedule). Other commonly observed adverse events include nausea and vomiting, anorexia, abdominal cramping, alopecia, asthenia, lymphocytopenia, and anemia. Dehydration has occurred as a consequence of diarrhea, particularly when associated with severe vomiting. Patients may have an acute syndrome of lacrimation, diaphoresis, abdominal cramping, and diarrhea (early diarrhea) during or shortly after irinotecan administration; this syndrome is thought to be cholinergically mediated, and may be treated and subsequently prevented with atropine. Sporadic cases of pulmonary toxicity, manifested as shortness of breath, non-productive cough and transient infiltrates on chest x-ray have been reported. Infrequent occurrences of mucositis or colitis (sometimes with gastrointestinal bleeding) have been observed. Occasionally, abnormalities of serum creatinine, hepatic enzymes, or thrombocytopenia have been observed.

Please refer to the package insert for further information regarding irinotecan.

**Concerns related to adverse effects:**

- Bone marrow suppression: [U.S. Boxed Warning]: May cause severe myelosuppression. Deaths due to sepsis following severe myelosuppression have been reported. Therapy should be temporarily discontinued if neutropenic fever occurs or if the absolute neutrophil count is  $<1000/\text{mm}^3$ . The dose of irinotecan should be reduced if there is a clinically significant decrease in the total WBC ( $<200/\text{mm}^3$ ), neutrophil count ( $<1500/\text{mm}^3$ ), hemoglobin ( $<8 \text{ g/dL}$ ), or platelet count ( $<75,000/\text{mm}^3$ ). Routine administration of a colony-stimulating factor is generally not necessary, but may be considered for patients experiencing significant neutropenia.
- Colitis: Colitis, complicated by ulceration, bleeding, ileus, and infection has been reported.

- Diarrhea: [U.S. Boxed Warning]: Severe diarrhea may be dose-limiting and potentially fatal; two severe (life-threatening) forms of diarrhea may occur. Early diarrhea occurs during or within 24 hours of receiving irinotecan and is characterized by cholinergic symptoms (eg, increased salivation, diaphoresis, abdominal cramping); it is usually responsive to atropine. Late diarrhea occurs more than 24 hours after treatment which may lead to dehydration, electrolyte imbalance, or sepsis; it should be promptly treated with loperamide. Patients with diarrhea should be carefully monitored and treated promptly.
- Hypersensitivity reactions: Severe hypersensitivity reactions have occurred.
- Renal toxicity: Renal impairment and acute renal failure have been reported, possibly due to dehydration secondary to diarrhea.
- Disease-related concerns:
- Bowel obstruction: Patients with bowel obstruction should not be treated with irinotecan until resolution of obstruction.
- Hepatic impairment: Use with caution in patients with hepatic impairment.
- Hyperbilirubinemia: Patients with even modest elevations in total serum bilirubin levels (1-2 mg/dL) have a significantly greater likelihood of experiencing first-course grade 3 or 4 neutropenia than those with bilirubin levels that were <1 mg/dL. Patients with abnormal glucuronidation of bilirubin, such as those with Gilbert's syndrome, may also be at greater risk of myelosuppression when receiving therapy with irinotecan. Use caution when treating patients with known hepatic dysfunction or hyperbilirubinemia; dosage adjustments should be considered.

### 7.3 Dose Modifications and Toxicity Management

All dose adjustments should be based on the worst preceding toxicity, graded using the National Cancer Institute Common Toxicity Criteria (version 4.0).

If more than one of the dose modifications apply, use the most stringent (i.e., the greatest dose reduction). Dose modifications are cumulative and permanent.

If treatment is held for any treatment-related toxicities for  $\geq 3$  weeks, patients should discontinue all protocol therapy.

The dose of leucovorin is not modified for toxicity, but is omitted if fluorouracil is omitted.

Dose modifications for toxicity are adapted from Conroy et al.

#### 7.3.1 Hematologic Toxicity

On day 1 of each cycle, hold all chemotherapy until the granulocyte count is  $\geq 1500/\mu\text{l}$  and the platelet count is  $\geq 75000/\mu\text{l}$ .

**Doses according to the blood counts at the beginning of a cycle (Day 1):**

BLOOD COUNTS DAY 1	DELAY OF CYCLE	DOSE REDUCTION		
		irinotecan	oxaliplatin	fluorouracil
Granulocytes <1500/<math>\mu</math>l	Hold treatment until granulocytes $\geq$ 1500/ $\mu$ l	1 st occurrence: reduce to 75% of previous dose  2 nd occurrence: maintain previous dose  3 rd occurrence: treatment discontinuation	1 st occurrence : no reduction  2 nd occurrence: reduce to 75% of previous dose  3 rd occurrence: treatment discontinuation	1 st occurrence: delete bolus 5FU
Platelets <75000/<math>\mu</math>l	Hold the treatment until platelets $\geq$ 75000	1 st occurrence: no reduction  2 nd occurrence: reduce to 75% of original dose  3 rd occurrence: treatment discontinuation	1 st occurrence: reduce to 75% of previous dose  2 nd occurrence: maintain previous dose  3 rd occurrence: treatment discontinuation	1 st occurrence: reduce bolus and infusion to 75% of previous doses

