**Doses for neutropenic fever or nadir cytopenias:**

ADVERSE EVENTS	REDUCTION OF DOSE FOR SUBSEQUENT CYCLES
Febrile neutropenia or Grade 4 neutropenia	1 st occurrence: reduce irinotecan to 75% of previous dose and delete the bolus 5FU dose  2 nd occurrence: reduce oxaliplatin to 75% of previous dose  3 rd occurrence: treatment discontinuation
Grade 4 thrombocytopenia	1 st occurrence: reduce oxaliplatin and 5FU (bolus and infusion) to 75% of previous dose  2 nd occurrence: reduce irinotecan and 5FU (bolus and infusion) to 75% of previous dose  3 rd occurrence: treatment discontinuation

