### 7.3.2 Diarrhea

Patients must be instructed in the use of loperamide for diarrhea, and must have a supply of this drug upon starting FOLFIRINOX. Patients should not be retreated with irinotecan until recovery from diarrhea to  $\leq$  grade1 (without loperamide for at least 24 h) has occurred. Diarrhea is attributed to chemotherapy UNLESS a specific infectious agent is isolated.

ADVERSE EVENTS	REDUCTION OF DOSE FOR SUBSEQUENT CYCLES
Diarrhea grade 3-4 or Diarrhea + fever and/or neutropenia grade 3-4	1 st occurrence: reduce irinotecan to 75% of previous dose and delete bolus 5FU dose  2 nd occurrence: reduce oxaliplatin and continuous infusion 5FU to 75% of previous doses  3 rd occurrence: treatment discontinuation
Diarrhea <math>\geq</math> 48 h despite high doses of loperamide	Hold FOLFIRINOX until resolves to $\leq$ grade1 for at least 24 hrs.  No dose reductions after complete recovery, unless gr 3-4 diarrhea, or diarrhea + fever and/or concomitant neutropenia gr 3-4

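### The irinotecan cut for a second low day-1 platelet count (7.3.1) is based on the original dose; read as the 135 mg/m² starting dose, it lowers no drug after one earlier irinotecan cut

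*Combined protocol and SAP*

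**What the plan says.** Section 7.3.1 of the combined protocol and SAP sets doses from the blood counts on day 1 of each cycle. In the row for platelets below 75,000/µl:

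- **Irinotecan:** no reduction at the first occurrence; at the second, "reduce to 75% of original dose"; at the third, treatment stops.
- **Oxaliplatin:** "reduce to 75% of previous dose" at the first occurrence; "maintain previous dose" at the second; stop at the third.
- **Fluorouracil:** "reduce bolus and infusion to 75% of previous doses" at the first occurrence; no second step is listed.

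The general rules at the start of section 7.3 cover all these tables. They state "Dose modifications are cumulative and permanent", and where several modifications apply the clinician is to "use the most stringent (i.e., the greatest dose reduction"). Sections 6.1 and 7.1 give the irinotecan starting dose as 135 mg/m². *Original* appears as a dose base in this one cell and is not defined.

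**The concern.** A cut measured from the starting dose is not cumulative. If irinotecan has already been reduced for another toxicity, the cell can ask for a dose that the patient is already receiving. Irinotecan is the only drug that the second-occurrence platelet step lowers, so the step would then have no effect.

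What is at stake is dosing safety. A clinician who follows the cell literally restarts all three drugs unchanged after a second low platelet count. One who follows the cumulative rule gives 25% less irinotecan. Both can point to the protocol.

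**Working it through.** **1. Count of the dose bases.** Each instruction in section 7.3 to reduce to 75%, counted as worded:

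| Place | Previous | Original |
|---|---|---|
| 7.3.1, day-1 blood counts | 4 | 1 |
| 7.3.1, neutropenic fever or nadir cytopenias | 4 | 0 |
| 7.3.2, diarrhea | 2 | 0 |
| 7.3.3, mucositis or hand-foot syndrome | 2 | 0 |
| 7.3.6, neurotoxicity | 2 | 0 |
| 7.3.7, other toxicities | 1 | 0 |
| Total | 15 | 1 |

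**2. Irinotecan dose under each base.** After k earlier cuts the current dose is 135 × 0.75^k. The starting-dose base gives 0.75 × 135 = 101.25 mg/m² whatever k is. The previous-dose base gives 0.75 × the current dose.

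| Earlier irinotecan cuts | Current dose | Starting-dose base | Previous-dose base |
|---|---|---|---|
| 0 | 135 | 101.25 | 101.25 |
| 1 | 101.25 | 101.25 (no change) | 75.94 |

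With one earlier cut the two bases differ by 101.25 − 75.94 = 25.31 mg/m², and 25.31 / 101.25 = 25%.

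**3. A path through the tables.** Starting doses in mg/m² are irinotecan 135, oxaliplatin 85, and 5-FU bolus 300 and infusion 2400.

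- Grade 3-4 diarrhea, first occurrence: "reduce irinotecan to 75% of previous dose and delete bolus 5FU dose". Irinotecan becomes 135 × 0.75 = 101.25; the bolus is dropped.
- First low day-1 platelet count: irinotecan stays at 101.25; oxaliplatin becomes 85 × 0.75 = 63.75; infusion becomes 2400 × 0.75 = 1800.
- Second low day-1 platelet count, starting-dose base: 101.25 / 63.75 / 1800. No drug is lowered.
- Second low day-1 platelet count, previous-dose base: 75.94 / 63.75 / 1800.

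A first low day-1 granulocyte count before the platelet events leads to the same irinotecan dose. If the earlier irinotecan cut came under section 7.3.7, the bolus is not deleted and stands at 300 × 0.75 = 225 after the first platelet event; the irinotecan comparison is the same.

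**4. Parallel second-occurrence rules.** In the granulocyte row of the same table, the second occurrence cuts oxaliplatin to 75% of the previous dose. At 63.75 that is 63.75 × 0.75 = 47.81. For a second grade 4 thrombocytopenia the rule is "reduce irinotecan and 5FU (bolus and infusion) to 75% of previous dose". From 101.25 and 1800 that gives irinotecan 75.94 and infusion 1800 × 0.75 = 1350. Both rules make a real further cut, and both use the previous dose.

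**The case against.** The best reply is that the opening rules of section 7.3 already settle the matter. Modifications are cumulative, so a careful clinician with a patient at 101.25 mg/m² would go to 75.94 mg/m². The section needs that kind of reading elsewhere: 7.3.7 keeps the other agents at full dose, which cannot mean undoing earlier permanent cuts. Within its own row the cell is also coherent, because the first platelet event leaves irinotecan alone. Without another toxicity, original and previous are the same dose.

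Much of this stands. The general rule does show which dose is probably intended, and the difference appears only when toxicities interact. But a general principle does not override the explicit base named in a specific cell. The rule on stringency chooses between modifications; it does not say which base one cell uses. It is also possible that *original* is deliberate, since section 7.3 says the rules are adapted from a cited trial. The documents neither say so nor give a reason for an exception in this one cell.

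Three further inferences are tempting, and the documents do not support them:

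- **Re-escalation.** After two earlier cuts the current dose is 135 × 0.75 × 0.75 = 75.94, and a literal 101.25 would be a 33% increase. The cell says to reduce, and section 7.3 makes modifications permanent, so this is not a fair reading.
- **A same-day path.** A reader might suppose that low granulocytes and low platelets on one day, then low platelets at the next cycle, is enough. That assumes the stringency rule is applied drug by drug, which section 7.3 does not say. If the platelet row alone governed the first event, irinotecan would still be 135 and both bases would give 101.25.
- **Another meaning of the word.** One could take *original* as the dose in force when the platelet events began. On the path above that would agree with the previous-dose base, but nothing in the protocol ties the word to that date.

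**Conclusion.** The point holds as a narrow wording error in a safety dosing rule. Followed as written, with *original* taken as the 135 mg/m² starting dose, the second-occurrence day-1 platelet step lowers no drug for a patient with one earlier irinotecan cut. A previous-dose base would give 25% less irinotecan (75.94 against 101.25 mg/m²). The cumulative rule and the parallel rows indicate that the further cut is intended.

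It affects only patients with an earlier irinotecan cut and two low day-1 platelet counts. It matters mainly in the 8 neoadjuvant cycles, since section 6.4 leaves further adjuvant modifications to the treating oncologist. The documents give no rate for this combination, so the number of patients cannot be stated. Other safeguards remain: the hold until platelets reach 75,000/µl, the 3-week limit on treatment holds, and the stop at a third occurrence. The primary endpoint definition, sample size, significance level and power are not touched.

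**What to change.** In the day-1 blood count table of section 7.3.1, irinotecan column, second platelet occurrence, change *original* to *previous*. With no earlier irinotecan cut the dose is still 101.25 mg/m²; with one it becomes 75.94 mg/m². If the starting dose is truly intended as the base, define it as 135 mg/m², add that the current dose applies if lower, and state the exception to the cumulative rule in section 7.3. The cost is one word, or one added clause and the stated exception.
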